2.1.1. Part A Period 4 Schedule of Activities

CONFIDENTIAL

								Ti	reatme	ent Peri	iod 4						Notes
Procedure	Day -10 (±3 days	24-48h Day -	Day						Day 1						Day 2	Day 3	If participants only take part in treatment Period 4 they will undergo screening assessments prior to this treatment Period
	(±3 days)	24-48h following Day -10 visit	ay -1	Pre-dose	0 h	15 mins	30 mins	1 h	2 h	3 h	4 h	6h	8 h	12 h	24 h	48 h	as detailed in Section 2.1.
Telemetry				<==	<=====> From 1 h pre-dose to 24 h post-dose. For receiving the LPS-challenge, telemetry in a minimum of 12 hours post-LPS or untit no clinically significant findings for 4 hour longer).												
Haematology			X									Х			Х	Х	24 and 48 hour samples will be taken prior to participants receiving breakfast
Coagulation												Х			Х	Х	24 and 48 hour samples will be taken prior to participants receiving breakfast
Clinical Chemistry			х									Х			Х	Х	24 and 48 hour samples will be taken prior to participants receiving breakfast
Urinalysis			х									Х			Х	Х	24 and 48 hour samples will be taken prior to participants receiving breakfast
Drug / Alcohol Test			Х														
Urine Cotinine			Х														
Visual forearm check (including cosmetic assessment)	x		х	See	Sectior	n 2.1.1			n 2.1.1 to cha			forearn					
AE / SAE review			SA	Es collec	ted fro	m sign	ing of	inform		sent fo st dose		Es colle	cted c	m time			
Concomitant Medication Review					Mo	onitore	d from	first do	ose un	til the e	end of	the fina	ıl treatı	ment P	eriod		

CONFIDENTIAL

								Tı	reatme	ent Peri	od 4						Notes
Procedure	Day -10 (±3 days)	24-48h Day -	Da						Day 1						Day 2	Day 3	If participants only take part in treatment Period 4 they will undergo screening assessments prior to this treatment Period
	±3 days)	24-48h following Day -10 visit	Day -1	Pre-dose	0 h	15 mins	30 mins	1 h	2 h	3 h	4 h	6h	8 h	12 h	24 h	48 h	as detailed in Section 2.1.
Treatment / agent adm	inistra	ation and	d PK s	ampling	1	1				1	1		1			1	
Study Drug / Placebo Administration					Х												
In vivo LPS Challenge							<==		===>								LPS administration to be performed at GSK3358699 systemic C _{max} ; anticipated to be between 0.5-2hrs post GSK3358699 dose.
OR in vivo GM-CSF Challenge							<==				==>						GM-CSF administration to be performed at GSK3358699 systemic C _{max} ; GM-CSF will be administered as an infusion over 2 hours and the start of the infusion is anticipated to be between 0.5-2hrs post GSK3358699 dose.

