Procedure	Screening (up to 45 Days prior to Day 1)	\pm (\pm 3 days)		Day -1	Day 1	Day 2	Day 3	Day 4	Day 5	Day 6	Day 7	Day 8	Day 9	Day 10	Day 11	Day 12	Day 13	Day 14	Day 15	Day 16	Follow-up 1 (7-14 days post-last dose)	2 (5 weeks) ose $\pm 3 days)$	The 2nd follow up visit is only required for those participants where challenges are being administered and blisters induced
																							point.
Telemetry					x			x				x						x					Continuous cardiac telemetry on each designated day from 1hr pre-dose until 24 h post-dose, and on other days if QTcF >450msec. For participants receiving the LPS-challenge, the Day 14 telemetry must be performed for a minimum of 12hrs post-LPS or until their telemetry shows no clinically significant findings for 4 hours (whichever is longer).
Holter monitoring (24 hours)	Х																						If a participant is rescreened the Holter will not need to be repeated.
HIV, Hep B, Hep C	Х																						
Haematology	х			x	x	х		x				x				x	x	x	х	x	х		Fasted screening samples. Sample to be taken pre-dose on Day 1, 2, 4, 8, 12 and 13. See Section 2.4.2 and Section 2.4.3 for haematology time points on Day 14, 15 and 16. Follow-up visit samples do not require fasting.
Coagulation	x			x				x				x					x	x			x		Fasted screening samples. Sample to be taken pre-dose on Day -1, 4, 8 and 13. See Section 2.4.2 for further details of Day 14 sample timings. Day 13 and Day 14 samples are only performed for subjects receiving LPS. Follow-up visit samples do not require fasting
Fasting lipids and glucose	x			x				x				x						x					Fasted screening samples. Sample to be taken pre-dose on each day. Both fasting lipids and glucose will be tested from same sample. Follow-up visit samples do not require fasting
Clinical Chemistry	x			x	х	х		x				x				x	х		Х	x	х		Fasted screening samples. Sample to be taken pre-dose on each day. Follow-up visit samples do not require fasting GGT and CK to be included at screening, Day-1 and follow up only.
Urinalysis	Х			х	Х	Х		Х				Х				Х				Х	Х		Fasted screening samples. Sample to be taken pre-dose on each day. Follow-up visit samples do not require fasting
Drug / Alcohol Test	Х			х																			Ad-hoc testing to be performed in the event of any cardiac arrhythmias, as close as possible to the time of occurrence
Urine Cotinine	Х			Х																			

2017N332348_05

CONFIDENTIAL

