Urine sample for metabolite analysis [E4]					x	x												x	x					A 0-24 urine collection will be made on Day 1 and Day 14. In each case, for the pre-dose sample, immediately prior to dosing participants will be instructed to void their bladder into a collection container. Following dosing participants will be instructed to collect all urine voided for a 0-24 hour collection.

2.4.1. Part C Day 14 Detailed SoA for Challenge Administration and PK Sampling Cohorts 4 and 8 (with challenges)

Procedure	Day 13	Pre-dose	Day 14 relatio		dose an he adm 30 mins						in 12 h	Day 15 24 h	Day 16 48 h	Notes
Treatment / agent administration	on and P	K sam	npling									-		
Study Drug / Placebo Administration			Х											
In vivo LPS Challenge					< =:					== >				LPS administration may be performed at low systemic GSK3358699 concs when intracellular levels of GSK3206944 are high; the decision on the timepoint will be based on emerging data and will be no more than 24hrs after dosing on Day 14.
OR in vivo GM-CSF Challenge					< ==		=====	=====			= >			GM-CSF administration may be performed at low systemic GSK3358699 concs when intracellular levels of GSK3206944 are high; the decision on the timepoint will be based on emerging data. GM-CSF will be administered as an infusion over 2 hours and the start of the infusion will be no more than 24hrs after dosing on Day 14.
Blood sampling for systemic PK [S1] and [S2]		Х		Х	Х	Х	Х	Х	Х	Х	Х	х	Х	Ad-hoc sample to be taken in the event of any cardiac arrhythmias, as close as possible to the time of occurrence
Blood sampling for intracellular PK [S3]	Х					х		х		х		х	Х	Pre-challenge samples. To be collected only until the start of challenge administration
Blood sample for ex vivo PD assay [S4]	х	х				x		x		x		x		Pre-challenge samples. To be collected only until the start of challenge administration.
Blood sample for circulating proteins [E1a]		х					х	х		х		х		Pre-challenge samples. To be collected only until the start of challenge administration.
Blood sample for gene panel [E1b]		х					х	x		х		х		Pre-challenge samples. To be collected only until the start of challenge administration.
Cantharidin application and PD sampling					See S	ection	2.4.2 a	and Se	ction 2	.4.3				

2.4.2. Part C Day 14 Detailed SoA for LPS Challenge and Biomarker Sampling Cohorts 4 and 8 (with challenges)

Procedure	Day 13				and all							Day 15	Day 16	
Tiocedure	13	Pre-dose	0 h	20 mins	1 h	2 h	3 h	4 h	6h	8 h	12 h	24 h	48 h	Notes

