	Observed adverse events were of mild severity and self- limiting without therapeutic intervention.	 Individuals with prior incidence of respiratory or cardiovascular diseases or pre-existing renal or hepatic dysfunction will be excluded from the study. In addition, we will use telemetry for a minimum of 6 hours following dosing, or until normal for 4 hours (whichever is longer). 		
		• Use of healthy volunteers is a mitigation for the fluid retention finding. In addition, a lower, single dose of GM-CSF is planned which means that the AUC and C_{max} will be lower than in the patients in which this was observed.		
	Topical Cantharidin Challenge Agent			
Irritation, burning or toxicity.	Cantharidin is a corrosive chemical substance which when used inappropriately may cause skin irritation, burning or toxicity.	 Cantharidin has been used clinically to treat warts and extensively in a clinical setting in experimental medicine studies to chemically induce blisters. Cantharidin will be used at a known concentration lower than has been safely explored in GSK sponsored studies conducted in patients and healthy participants, (ie reduced in this study from 0.7% to 0.2 %). Participants with a history of lymphangitis and/or lymphoedema or any participant who has undergone surgery resulting in loss of tissue associated with lymphoid drainage (e.g. certain breast surgery procedures) are excluded. Participants will be advised to wear loose clothing at the site of blistering to minimise hyperaesthesia and discomfort that may occur. 		

Potential Risk of Clinical Significance	Summary of Data / Rationale for Risk	Mitigation Strategy
		 For immediate relief of any discomfort, paracetamol, at doses of ≤2 grams/day will be given to the participant, unless, in the opinion of the investigator and sponsor, the medication will interfere with the study.
		• Participants with history of keloids, skin allergy, hypersensitivity, or contact dermatitis, including previous reactions to dressings to be used in this study or any chronic skin disorder (e.g. psoriasis, atopic dermatitis, vitiligo) excepting isolated lesions remote from intended site of application of cantharidin are excluded. Appropriate skin care to avoid dyspigmentation and hypertrophic scar will be implemented.

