5.5.3. Part C

Five dosing cohorts are planned for Part C. Once-daily dosing (QD) of GSK3358699 is planned for 14 consecutive days in Cohorts 4 - 7 and for up to 14 consecutive days in Cohort 8. The selection of appropriate doses will be performed upon consideration of

available safety and tolerability, PK and PD data from Part A and/or any preceding repeat dose cohorts in Part C.

The dose of GM-CSF to be administered to participants in Part C will be 60 μ g/m². The dose of LPS to be administered to participants in Part C will be 0.75 ng/kg.

Administration of the challenge agents will be on Day 14 in Cohort 4 and is planned to be on the final day of dosing in Cohort 8; the time point will be based on an estimate of the intracellular acid kinetics determined in the preceeding cohorts of the study and will be no more than 24 h after dosing with GSK3358699 or placebo on that day.

Based on emerging data, the DEC may decide to modify the dosing frequency to less than once daily or more than once daily, as well as make other modifications as detailed in Section 7.2.

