9. STUDY ASSESSMENTS AND PROCEDURES

- Study procedures and their timing are summarized in the SoA. Acceptable time windows around the nominal time points for specific assessments will be included in the SRM and assessments performed within these time windows will not constitute a protocol deviation.
- Protocol waivers or exemptions are not allowed
- Immediate safety concerns should be discussed with the sponsor immediately upon occurrence or awareness to determine if the participant should continue or discontinue study treatment.
- Adherence to the study design requirements, including those specified in the SoA, is essential and required for study conduct.
- All screening evaluations must be completed and reviewed to confirm that potential participants meet all eligibility criteria. The investigator will maintain a screening log to record details of all participants screened and to confirm eligibility or record reasons for screening failure, as applicable.
- The maximum amount of blood collected from each participant over the duration of the study, including any extra assessments that may be required, is not planned to exceed 500 mL.
- Repeat or unscheduled samples may be taken for safety reasons or for technical issues with the samples.

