9.4.6. Cardiac Telemetry

Continuous cardiac telemetry will be performed in the study at the time points detailed in the SoA and at other times in the study if clinically indicated as detailed in the SoA (Section 2.3).

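### The 6 h telemetry minimum after GM-CSF in Protocol Section 3.3.1 is not carried into the Cohort 4/8 schedule, so infusions starting more than 16–18 h after the Day 14 dose can miss it

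*Protocol*

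**What the plan says.** **The commitment.** In the GM-CSF part of the risk table (Protocol Section 3.3.1), the mitigation column says "we will use telemetry for a minimum of 6 hours following dosing, or until normal for 4 hours (whichever is longer"). The corresponding LPS entry counts its telemetry from the LPS dose, so dosing here is most naturally read as GM-CSF dosing.

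**The schedule.** The telemetry row for Cohorts 4 and 8 (Section 2.4) reads "Continuous cardiac telemetry on each designated day from 1hr pre-dose until 24 h post-dose, and on other days if QTcF >450msec". It then adds a rule timed from the challenge for one agent only: "For participants receiving the LPS-challenge, the Day 14 telemetry must be performed for a minimum of 12hrs post-LPS", or until there have been 4 h without clinically significant findings if that is later. GM-CSF has no such rule. The detailed GM-CSF schedule (Section 2.4.3) contains no telemetry row.

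**When GM-CSF may be given.** For Part C, Section 2.4.1 says "the start of the infusion will be no more than 24hrs after dosing on Day 14", and the infusion lasts 2 h. Section 5.5.3 repeats the limit: the challenge time point "will be no more than 24 h after dosing with GSK3358699 or placebo on that day". In Part A Period 4 (Section 2.1.1), "the start of the infusion is anticipated to be between 0.5-2hrs post GSK3358699 dose".

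**Which text governs.** Section 9 states: "Adherence to the study design requirements, including those specified in the SoA, is essential and required for study conduct". Section 9.4.6 refers telemetry to the schedule, and otherwise to telemetry "at other times in the study if clinically indicated as detailed in the SoA (Section 2.3"). Section 2.3 is the table for Cohorts 5–7, which have no challenge.

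**The concern.** The risk section promises monitoring counted from the GM-CSF challenge, while the schedule that the site must follow counts from the study drug. The two agree only if the challenge comes early enough. In Part C it may be given late by design: Section 5.4 allows the challenge to be timed to low systemic drug and high intracellular metabolite, with a predicted systemic half-life of about 3 h. Section 7.2 also lets the timing change as data emerge.

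A site working from the telemetry row could stop monitoring a GM-CSF participant before the promised 6 h, or while the trace is still abnormal. The risk table names cardiovascular symptoms as a GM-CSF risk. The four ventricular tachycardia episodes behind Amendment 4 were asymptomatic, so monitoring prompted by symptoms could miss a recurrence. The protocol already writes the equivalent protection into the row for LPS, including in Part A Period 4, where 12 h after an LPS dose at 0.5–2 h falls well inside the 24 h window anyway. The omission for GM-CSF therefore looks like a drafting slip.

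**Working it through.** The plan states no figure of its own for this gap. The check is interval arithmetic on its time limits.

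**Inputs**
- End of scheduled telemetry: 24 h after the study-drug dose (Section 2.4)
- Promised minimum: 6 h after GM-CSF (Section 3.3.1)
- Infusion length: 2 h (Section 2.4.1)
- Latest permitted start in Part C: 24 h post-dose (Sections 2.4.1 and 5.5.3)
- Anticipated start in Part A: 0.5–2 h post-dose (Section 2.1.1)

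Section 3.3.1 does not say whether the 6 h runs from the start or the end of the infusion, so both readings are shown.

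**Formulas**, with the infusion starting s hours post-dose
- Telemetry left from infusion start: 24 − s. The minimum is met if 24 − s ≥ 6, so s ≤ 18 h.
- Telemetry left from infusion end: 24 − (s + 2) = 22 − s. The minimum is met if 22 − s ≥ 6, so s ≤ 16 h.
- Telemetry end time needed: s + 6 (from start) or s + 8 (from end).

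| Start s (h) | Left from start (h) | Left from end (h) | End time needed, start / end reading (h) | 6 h minimum met? |
|---|---|---|---|---|
| 2 (latest anticipated in Part A) | 22 | 20 | 8 / 10 | yes / yes |
| 12 | 12 | 10 | 18 / 20 | yes / yes |
| 16 | 8 | 6 | 22 / 24 | yes / yes |
| 18 | 6 | 4 | 24 / 26 | yes / no |
| 20 | 4 | 2 | 26 / 28 | no / no |
| 22 | 2 | 0 | 28 / 30 | no / no |
| 24 (limit) | 0 | none | 30 / 32 | no / no |

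The permitted starts that miss the minimum are those after 18 h and up to 24 h (from start), or after 16 h and up to 24 h (from end).

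**The second condition.** The requirement to continue until the trace has been normal for 4 h does not depend on s. It appears in neither the Section 2.4 row nor the Section 2.1.1 row. In Part A this is the only thing missing, because at least 20 h of telemetry follows the end of the infusion.

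**Participants.** The plan assigns GM-CSF to 7 of 14 participants in Cohort 4 and 10 of 20 in Cohort 8.

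**The case against.** The strongest reply is that late starts are an outer limit and not the working plan. The GM-CSF arrow in the Section 2.4.1 grid appears to stop near the 12 h column, though the table is broken in extraction. A 12 h start leaves 10–12 h of telemetry. The challenge is marked on Day 14, with the pre-dose sample at about 08:00. If Day 14 means the calendar day, the latest start is about 16 h post-dose, which passes. A 24 h start would also push the 48 h post-challenge assessments and blister harvest past Day 16. This shows that the gap lies at the edge of the permitted range. It does not close it, because two sections state the 24 h limit explicitly. The same grid also lists pre-challenge samples at 24 h that are to stop once the challenge begins. That is supporting evidence only, since the intracellular row carries a 48 h mark as well.

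Other safeguards exist. Participants remain in the unit through the 48 h assessments. Vital signs are timed from GM-CSF, and ECGs are taken on Days 14 to 16. Telemetry can be added if clinically indicated, and Section 2 allows assessments to be retimed without an amendment. Nothing makes 24 h a maximum, so a site that also reads Section 3.3.1 could satisfy both texts. All of this lowers the risk, but none of it is a required telemetry minimum.

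Two points stand in full. Cohort 4 was terminated on 14 November 2018 (SAP Section 13.6.1), before Amendment 4 of 11 December 2018, so its 7 GM-CSF participants are a planned count that this version could not affect. The Section 9.4.6 cross-reference is editorial.

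**Conclusion.** The concern holds. Followed as written, the Cohort 4/8 telemetry row can give less cardiac monitoring after GM-CSF than Section 3.3.1 promises. The shortfall begins at starts after 18 h or 16 h, depending on where the 6 h is counted from, and reaches zero coverage at the permitted 24 h limit. The normal-trace condition is missing at all start times, in Part A as well as Part C. The conclusion assumes that dosing in the GM-CSF entry means GM-CSF dosing, and that the explicit 24 h limit overrides the apparent 12 h arrow.

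This should be corrected, but it is not a fault that undermines the trial. Starts up to 16 h meet the 6 h minimum on either reading. The SAP (Section 2.3) records that in Part C only Cohorts 4 and 5 were dosed, so no Cohort 8 participant was exposed to the gap.

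**What to change.** Add a GM-CSF sentence to the telemetry rows of Sections 2.4 and 2.1.1, parallel to the LPS text. For example: *GM-CSF participants stay on telemetry for at least 6 h after the infusion ends, or until the trace has been normal for 4 h if that takes longer.* Counting from the end of the infusion is the more protective reading. If the sponsor means 6 h from the start, Section 3.3.1 and both rows should say so. Extend the Section 9.4.6 reference to include Section 2.4.

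The cost is one sentence in each of two rows and one cross-reference. For the 6 h minimum, the largest extension is (24 + 2 + 6) − 24 = 8 h of telemetry per GM-CSF participant, and none for starts up to 16 h. It is longer only if the trace is not normal. Participants are already in the unit for the 48 h assessments, so the 6 h minimum adds no inpatient time. Capping the GM-CSF start at 16 h post-dose would also secure the 6 h minimum, but it would restrict the timing and would still leave out the normal-trace condition.

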3.3.2. Benefit Assessment

There will be no direct benefit to the healthy participants in this trial. However, the information obtained from this study will critically inform the conduct of future clinical studies to develop new therapies in immuno-inflammation indications in areas of unmet medical need.

3.3.3. Overall Benefit:Risk Conclusion

Taking into account the measures taken to minimize risk to participants participating in this study, the potential risks identified in association with GSK3358699, LPS, GM-CSF and cantharidin at the doses to be administered are considered minimal and are justified.

4. OBJECTIVES AND ENDPOINTS

Objectives	Endpoints	
Primary		
• [P1] To evaluate the safety and tolerability of single and repeat oral doses of GSK3358699 in healthy male participants.	 AE reporting. Laboratory safety data (clinical chemistry, haematology, urinalysis). Vital signs (blood pressure, heart rate, body temperature). 12 lead ECGs. 	
Secondary		
• [S1] To evaluate the systemic pharmacokinetic (PK) profile following single and repeat oral doses of GSK3358699 in healthy male participants.	 Plasma concentrations of GSK3358699 plus derived PK parameters. 	
• [S2] To evaluate the systemic PK profile of the acid metabolite, GSK3206944 following single and repeat oral doses of GSK3358699 in healthy male participants.	 Plasma concentrations of GSK3206944 plus derived PK parameters. 	
• [S3] To evaluate the intracellular PK profile of GSK3206944 in target cells following single and repeat oral doses of GSK3358699 in healthy male participants.	 Monocyte intracellular quantification of GSK3206944. 	
• [S4] To understand the extent of target engagement (TE) after ex vivo LPS challenge following single and repeat oral doses of GSK3358699 in healthy male participants.	 Plasma concentrations of monocyte chemoattractant protein (MCP)-1, interleukin (IL)-6 and tumour necrosis factor (TNF) in blood stimulated ex vivo with LPS over time. 	
• [S5] To assess the effect of food on the PK and PD of GSK3358699 and GSK3206944 following single doses in healthy male participants.	 Plasma concentrations of GSK3358699 and GSK3206944 plus derived PK parameters. Monocyte intracellular quantification of GSK3206944. 	

Objectives	Endpoints
	 Plasma concentrations of MCP-1, IL-6 and TNF in blood stimulated ex vivo with LPS over time.
Exploratory	
• [E1] To investigate effects on basal production of biomarkers of target engagement following single and repeat oral doses of GSK3358699 in healthy male participants.	• Time course of circulating leukocyte numbers and circulating proteins; may include but is not limited to MCP-1, IL-12p40 and matrix metallopeptidase (MMP)-9.
	Gene panel using participant whole blood.
• [E2] To investigate effects on inflammatory biomarkers after low dose in vivo LPS or GM-CSF challenge following single and repeat oral doses of GSK3358699 in	 Time course of circulating soluble inflammatory biomarkers; may include but is not limited to IL-1β, IL-6, IL-8, TNF, MCP-1, GM-CSF, C-reactive protein (CRP).
healthy male participants.	 Time course of leukocyte numbers and cellular activation markers may include, but not limited to expression of cluster of differentiation (CD) molecules CD16, CD86, CD80, CD163, CD206, CD83, CD40, CD209, Human Leukocyte Antigen – antigen D Related (HLA-DR) in circulating leukocytes.
	Gene panel using participant whole blood.
• [E3] To investigate effects on chemotaxis and inflammatory mediators in cantharidin- induced blisters following single and repeat oral doses of GSK3358699 in healthy male participants.	 Soluble inflammatory biomarkers in skin blisters; may include but is not limited to IL- 1β, IL-6, IL-8, TNF, MCP-1, GM-CSF. Blister volumes and differential cell counts; cellular activation markers that may include, but not limited to expression of CD16, CD86, CD80, CD163, CD206, CD83, CD40, CD209, HLA- DR in blister leukocytes.
• [E4] To collect residual plasma following GSK3358699 & GSK3206944 analysis, and urine samples, for analysis of metabolites of GSK3358699	 Metabolites of GSK3358699 in plasma and urine. These analyses will be run and reported under a separate protocol.
• [E5] To explore the impact of CES genetic variation on PK and PD parameters of GSK3358699 and GSK3206944.	 Genotype results using participant whole blood.

- P1: Primary Objective 1 Safety
- S1: Secondary Objective 1 GSK3358699 systemic PK
- S2: Secondary Objective 2 GSK3206944 systemic PK
- S3: Secondary Objective 3 GSK3206944 intracellular PK
- S4: Secondary Objective 4 TE
- S5: Secondary Objective 5 Effect of food on PK and PD
- E1: Exploratory Objective 1 Effect on basal production of biomarkers of TE
- E2: Exploratory Objective 2 Effects on inflammatory biomarkers after low dose in vivo LPS or GM-CSF challenge
- E3: Exploratory Objective 3 Biomarkers in blisters
- E4: Exploratory Objective 4 PK metabolite analysis
- E5: Exploratory Objective 5 CES genetic variation

